5.4.2 Safety Analyses

Safety analyses will be performed on the SafAS and presented by group for all participants and by age group for summary tables (main endpoints). The main parameters will be described with 95% CI. At least the number and percentages of participants will be presented after vaccine injection reporting any:

- Immediate unsolicited systemic AEs.
- Solicited injection site reactions and solicited systemic reactions occurring within 7 days after the day of injection (D01 to D08) according to presence, time of onset, intensity (Grade 1, Grade 2, or Grade 3), number of days of presence and action taken.
- Unsolicited AEs occurring within 30 days after injection by SOC and PT, relationship, intensity, time of onset, and duration.
- All SAEs that occur throughout the study by SOC and PT, relationship and seriousness criteria.
- All AESIs that occur throughout the study by SOC and PT and relationship.

5.4.3 Immunogenicity Analyses

The immunogenicity analyses will be performed first on the PPAS and then on the FAS.

The point estimates and their 95% CI of the following parameters will be presented by group for all participants and by age group before and one month post-vaccination for each pneumococcal serotype specific OPA titers and IgG concentrations:

- GMT/GMC of serotype specific titers/concentrations.
- GMT/GMC ratio (post/pre-vaccination).

In addition, the following analyses will be presented:

- Differences in terms of ratio of GMTs/GMCs between 2 groups (for instance, any SP0202 formulations and Prevnar 13 or Pneumovax 23) and 95% CI at 1-month post-vaccination on all participants and by age group.
- Percentages of participants with titers/concentrations above certain thresholds and achieving several X-fold from pre to post-vaccination.
- Several graphical representations (in a log10 scale) will be used for all serotypes by group for all participants and by age group:
 - RCDCs of individual OPA titers and IgG concentrations at pre and 1-month post-vaccination.
 - Forest plots of GMTs or GMCs at pre and 1-month post-vaccination.
 - Forest plots of GMT/GMC ratio between groups at 1-month post-vaccination.
 - Boxplots of the OPA titers and IgG concentrations at pre and 1-month post-vaccination.

Table 5.2: Summary of statistical analyses for immunogenicity analysis

Endpoint	Visit and Age group	Description
Serotype-specific pneumococcal OPA titer for each of the 21 serotypes	V01 and V02 - all participants	OPA GMT and 95% CI, corresponding Forest Plot
	V01 and V02 - 50-64 years	
	V01 and V02 - 65-84 years	
	V02/V01 - all participants	OPA GMT ratio (post/pre) and 95% CI
	V02/V01 - 50-64 years	
	V02/V01 - 65-84 years	
	V02/V01 - all participants	Percentage of participants with titers at V02 \geq 2/4/8/16-fold rise over V01 and 95% CI and <LLOQ at V01 to \geq LLOQ at V02
	V02/V01 - 50-64 years	
	V02/V01 - 65-84 years	
	V02 - all participants	OPA GMT ratio and 95% CI and corresponding Forest Plot between:
	V02 - 50-64 years	
 - each SP0202 formulation (ie, SP0202-VI/SP0202-IIb, SP0202-VII/SP0202-IIb, SP0202-VII/SP0202-VI) - any SP0202 group and Prevnar 13 or Pneumovax 23 (ie, SP0202-IIb/Prevnar 13, SP0202-VI/Prevnar 13, SP0202-VII/Prevnar 13; SP0202-IIb/Pneumovax 23, SP0202-VI/Pneumovax 23, SP0202-VII/Pneumovax 23)
	V02 - 65-84 years	
	V01 and V02 - all participants	OPA titer RCDC
	V01 and V02 - 50-64 years	
	V01 and V02 - 65-84 years	
	V01 and V02 - all participants	OPA titers boxplot
	V01 and V02 - 50-64 years	
	V01 and V02 - 65-84 years	
Serotype-specific pneumococcal IgG concentration for each of the 21 serotypes	V01 and V02 - all participants	IgG GMC and 95% CI, corresponding Forest Plot
	V01 and V02 - 50-64 years	
	V01 and V02 - 65-84 years	
	V02/V01 - all participants	IgG GMC ratio (post/pre) and 95%CI
	V02/V01 - 50-64 years	
	V02/V01 - 65-84 years	
	V02/V01 - all participants	Percentage of participants with concentrations at V02 \geq 2/4/8/16-fold rise over V01 and 95% CI and <LLOQ at V01 to \geq LLOQ at V02
	V02/V01 - 50-64 years	
	V02/V01 - 65-84 years	

	V02 - all participants V02 - 50-64 years V02 - 65-84 years	IgG GMC ratio and 95% CI and corresponding Forest Plot between: - each SP0202 formulation (ie, SP0202-VI/SP0202-IIb, SP0202-VII/SP0202-IIb, SP0202-VII-SP0202-VI) - any SP0202 group and Prevnar 13 or Pneumovax 23 (ie, SP0202-IIb/Prevnar 13, SP0202-VI/Prevnar 13, SP0202-VII/Prevnar 13; SP0202-IIb/Pneumovax 23, SP0202-VI/Pneumovax 23, SP0202-VII/Pneumovax 23)
	V01 and V02 - all participants V01 and V02 - 50-64 years V01 and V02 - 65-84 years	IgG concentration RCDC
	V01 and V02 - all participants V01 and V02 - 50-64 years V01 and V02 - 65-84 years	IgG concentration boxplot

5.4.4 Other analyses

COVID-19

Impact of COVID-19 pandemic on study conduct and disposition of participants impacted by COVID-19 pandemic situation will be summarized in tables on all participants and by age group and listed in Appendix 16 of the CSR.

If more than 10% of randomized participants are impacted by COVID-19, and still evaluable for immunogenicity/safety timepoints, additional analyses in impacted/non-impacted participants will be done on main immunogenicity and safety endpoints.

In addition, in case the 2019-nCOV serostatus is determined for the participants (see Section 4.2 of the protocol), at minimum, results will be presented for tested participants.

Subgroup Immunogenicity analyses

Additional analyses will be done according to gender (two categories: Male, Female), race (two categories: the modality[ies] the most represented versus the pool of the other modalities) and IgG/OPA baseline LLOQ status (ie, <LLOQ or \geq LLOQ) on the main parameters:

- GMT/GMC of serotype specific titers/concentrations
- GMT/GMC ratio (post/pre-vaccination)

Baseline adjusted Immunogenicity analyses

In addition to GMT/GMCs ratio between groups, GMTs/GMCs ratio will be computed using constrained Longitudinal Data Analysis (cLDA) model (3).

CLDA will be used to take into account baseline titer/concentration in the model. This approach assumes that the baseline mean values are equal between all groups (reasonable assumption because of the randomization).

Correlation heatmap Immunogenicity analyses

Correlation heatmaps will be plotted for both serotype specific IgG concentrations and serotype specific OPA titers at post-vaccination using the Spearman's correlation matrix across serotypes. One figure for each group separately will be plotted, and one figure pooling the three SP0202 groups will be plotted as well.

All the 'Other analyses' will be conducted in the FAS and provided in Appendix 15 of the CSR.

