5.3 Population for Analyses

Population	Description
Randomized	All participants with data in the CRF
Safety Analysis Set (SafAS)	Participants who have received the study vaccine. All participants will have their safety analyzed according to the vaccine they actually received. Safety data recorded for a vaccine received out of the protocol design will be excluded from the analysis (and listed separately).
Full analysis set (FAS)	Subset of randomized participants who received at least 1 dose of the study vaccine and had a valid post-vaccination blood sample result (serotype specific IgG concentration or serotype specific OPA titer for at least one serotype). Participants will be analyzed according to the intervention to which they were randomized.
Per-protocol analysis set (PPAS)	
Subset of the FAS. Participants presenting with at least one of the following relevant protocol deviations will be excluded from the PPAS:
 
 • Participant did not meet all protocol-specified inclusion criteria or met at least one of the protocol-specified exclusion criteria • Participant did not receive vaccine • Participant received a vaccine other than the one that he / she was randomized to receive • Preparation and / or administration of vaccine was not done as per-protocol • Participant did not provide the post-dose serology sample at V02 in the proper time window or a post-dose serology sample was not drawn • Participant received a protocol-prohibited therapy / medication / vaccine 
In addition to the reasons listed above, participants will also be excluded from the PPAS if their Visit 02 / post-vaccination serology sample did not produce a valid test result (ie, results for all pneumococcal serotypes for both OPA and IgG are missing).
 
In the event of a local or national immunization program with a pandemic influenza vaccine, participants who receive 1 or more doses of a pandemic influenza vaccine at any time during the study will not be withdrawn from the study.
 
As the COVID-19 vaccination campaign has been deployed during the study period, participants who receive 1 or more doses of COVID-19 vaccine during the study period will not be withdrawn from the study.

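### Read literally, SAP 5.4.4 puts the conditional COVID-19 safety comparison on the FAS, against the SafAS rule in SAP 5.4.2, and leaves the population for COVID-19 disposition inconsistent

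*SAP*

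**What the plan says.** SAP 5.4.4 has four parts: COVID-19, subgroup immunogenicity analyses, baseline-adjusted immunogenicity analyses and correlation heatmaps for immunogenicity. The COVID-19 part makes two plans that matter here.

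- Pandemic impact on study conduct, and the disposition of impacted participants, "will be summarized in tables on all participants and by age group and listed in Appendix 16 of the CSR".
- A conditional comparison is also planned, under which "additional analyses in impacted/non-impacted participants will be done on main immunogenicity and safety endpoints". Whether it runs at all depends on a trigger that the SAP words as follows: "If more than 10% of randomized participants are impacted by COVID-19, and still evaluable for immunogenicity/safety timepoints".

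The section closes with one sentence on population for everything in it: "All the 'Other analyses' will be conducted in the FAS and provided in Appendix 15 of the CSR". No exception is written for the COVID-19 part.

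SAP 5.3 defines the FAS as "Subset of randomized participants who received at least 1 dose of the study vaccine and had a valid post-vaccination blood sample result". One IgG or OPA result for one serotype is enough, and participants are analysed as randomized. The SafAS requires only that study vaccine was received, and it analyses participants by the vaccine actually given. SAP 5.4.2 is unqualified: "Safety analyses will be performed on the SafAS".

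**The concern.** The closing sentence suits three of the four parts, because those three concern immunogenicity only. The COVID-19 part is the only one that includes safety endpoints, and there the sentence sets a population that conflicts with SAP 5.4.2.

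The conflict has a practical effect. A vaccinated participant who never gives a usable post-vaccination sample can still have safety data. Immediate events are recorded on D01, SAEs and AESIs are collected for 6 months, and a D181 telephone call is planned. Protocol 7.2 asks sites to attempt the scheduled safety follow-up of early terminators unless they refuse contact or are lost to follow-up. Such a person is in the SafAS but not in the FAS.

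Missing Visit 2 is a plausible way of being impacted by the pandemic. A programmer who follows 5.4.4 as written would therefore apply an entry condition that impacted participants may fail more often than others, in the comparison meant to describe them. Anyone given the wrong vaccine would also be counted, for safety, under a vaccine not received.

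**Working it through.** **1. The plan's own figure.** The closest number is the evaluable count in SAP 5.2: 150 × (1 − 0.15) = 127.5, rounded to 128 per group. It reproduces and is not in dispute. It refers to the PPAS. The documents give no expected number of participants without a sample, and none for pandemic-related losses.

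**2. The rules side by side.**

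| | FAS (SAP 5.3, applied by 5.4.4) | SafAS (SAP 5.3, applied by 5.4.2) |
|---|---|---|
| Vaccinated | required | required |
| Valid post-vaccination IgG or OPA result | at least one serotype | not required |
| Visit 2 window | no condition | no condition |
| Group used | as randomized | vaccine received |

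The visit-window exclusion belongs to the PPAS only. A late Visit 2 sample with any valid result keeps the participant in the FAS. Only a sample never drawn, or one with no valid result at all, removes the participant.

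**3. Consistency within 5.4.4.** The condition for the COVID-19 comparison speaks of participants still evaluable for immunogenicity/safety timepoints. The natural reading includes people evaluable for safety only. The FAS rule removes exactly those people.

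**4. Disposition.** The COVID-19 paragraph refers to all participants and to Appendix 16. The closing sentence says FAS and Appendix 15. The first phrase does not settle the set, because SAP Table 5.2 uses it for the two age groups combined within whichever population is being analysed. SAP 5.4.1 summarises general disposition without naming a set.

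**5. Size, as a range.** The boundary of the trigger is 0.10 × 750 = 75 impacted participants. Assume that all 75 are vaccinated and have some safety data, that everyone else is in the FAS, and that a share *m* of the 75 has no valid post-vaccination result.

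- Impacted participants kept in the FAS = 75 × (1 − *m*)
- Impacted share of the FAS = 75(1 − *m*) / (750 − 75*m*)

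| Assumed *m* | Kept in FAS | Impacted share of FAS | Kept in SafAS |
|---|---|---|---|
| 0% | 75 | 10.0% | 75 |
| 25% | 56 | 7.7% | 75 |
| 50% | 38 | 5.3% | 75 |
| 75% | 19 | 2.7% | 75 |
| 100% | 0 | 0% | 75 |

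As a separate illustration, if the whole planned 15% drop-out consisted of vaccinated participants without a valid sample, 0.15 × 750 = 112.5, or about 112 people, would be in the SafAS and outside the FAS. Nothing in the documents says that it would.

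**The case against.** The strongest reply is that this is loose drafting with little consequence. Three of the four parts are labelled as immunogenicity analyses, so the author probably had those in mind. The study is descriptive and tests no hypotheses. The comparison runs only if the 10% trigger is met. The main safety tables stay on the SafAS, so these participants' events are still reported there. All of this stands, and it limits the weight of the point. It does not remove the conflict, because the sentence covers every analysis in the section without exception.

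A second reply is that the SafAS would recover less than it seems. The diary card is reviewed and collected at Visit 2, and SAP 4.3.1.1.3 drops participants with no recorded presence for a solicited endpoint. For someone who never attends Visit 2, much of the solicited and 30-day unsolicited data may be absent under any population. That also stands. What remains is immediate AEs, SAEs, AESIs and any diary data that the site recovers.

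A reader might infer three stronger things that the documents do not support:

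- *The disposition table is on the FAS and so omits those lost to COVID-19.* The text points both ways, so the population is contradictory and not plainly the FAS.
- *Anyone who misses the Day 31 window is excluded.* The FAS has no window.
- *Impacted participants will be made to look like the others.* This needs a link between lacking a sample and safety outcome, and none is given.

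**Conclusion.** The point holds for safety. SAP 5.4.4 sets a population for the COVID-19 safety comparison that contradicts SAP 5.4.2 and does not fit the section's own evaluability wording. This is a wrong rule and not merely a missing detail, since following it would drop vaccinated participants with safety data and would group by randomization. For COVID-19 conduct and disposition, the finding is an inconsistency of population and appendix. For the immunogenicity part the FAS does no harm, because a person without a sample has no post-vaccination value to contribute.

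The size cannot be fixed from the documents. The range of 75 down to 0 retained out of 75 rests on assumed shares and on every impacted participant being vaccinated with some safety data. The direction of any bias is unknown. The correction should be made, but the main safety conclusions do not depend on it.

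**What to change.** Replace the closing sentence of SAP 5.4.4 with text to this effect:

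- The immunogenicity analyses in this section, including the COVID-19 immunogenicity comparison, use the FAS.
- The COVID-19 impacted/non-impacted safety analyses use the SafAS, by vaccine actually received.
- COVID-19 impact on study conduct and disposition is summarised on all randomized participants, overall and by age group.
- State which COVID-19 outputs go to Appendix 15 and which to Appendix 16 of the CSR.

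The cost is a few lines in the SAP and a change of population flag in the programs for the COVID-19 safety and disposition outputs. No new data are needed.

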5.5 Handling of Missing Data and Outliers

5.5.1 Safety

Generally, no replacement will be done. However, imputations may be done for a limited number of scenarios, some of which are described in this section. In all participant listings, partial and missing data will be clearly indicated as missing.

5.5.1.1 Immediate

For unsolicited systemic AEs, a missing response to the "Immediate" field is assumed to have occurred after the 30-minute surveillance period and will not be imputed.

5.5.1.2 Causal relationship

By convention, all events reported at the injection site (either solicited or unsolicited) will be considered as related to the administered product and then referred to as reactions. In a same way, all solicited systemic events pre-listed in the CRF are also considered as related to vaccination and will be considered as reactions.

- For unsolicited systemic AE, missing relationship will be considered as related to investigational product at the time of analysis.
- The missing relationship to study procedures for SAEs will not be imputed.

5.5.1.3 Intensity

For solicited reactions, missing intensities will be handled as described in [Section 4.3.1.1](#). For unsolicited AEs, missing intensities will remain missing and will not be imputed.

5.5.1.4 Start Date and Stop Date

Missing or partially missing start dates or end dates for unsolicited AEs (including SAEs) will remain missing and not be imputed. If the start date is missing or partially missing, the time of onset will be considered to be missing. Nevertheless, unsolicited AEs with missing time of onset will be included in analyses according to the visit number collected in "Appeared after visit" or

similar field. If either the start date or end date is missing or partially missing, the duration will be considered missing.

Missing or partially missing end dates for ongoing solicited AEs will remain missing and not be imputed.

5.5.1.5 Action Taken

Missing actions taken will remain missing and not be imputed.

5.5.2 Immunogenicity

Missing data will not be imputed. No test or search for outliers will be performed.

LLOQ and ULOQ management will be performed as described in [Section 4.3.2.1](#) and [Section 4.3.2.3](#).

5.5.3 Efficacy

Not applicable

5.6 Interim / Preliminary Analysis

This study will not include an early safety data review. However, participant safety will be continuously monitored by the Sponsor's internal safety review committee which includes safety signal detection at any time during the study. The analysis for SMT will be blinded and descriptive therefore no statistical adjustment is necessary.

A DMC (Data Monitoring Committee) will review continuously any related AESIs and related SAEs until the end of the 6-month follow-up. In addition, a first DMC safety analysis on data collected on at least 150 participants up to D31 (30 days after injection) will be conducted in an unblinded manner by an external independent statistician to Sanofi and will not be communicated to the Sponsor. The DMC will also review the unblinded safety data collected up to D31 on all participants. The analyses for this scope will be descriptive so no statistical adjustment is necessary.

A statistical analysis of the safety and immunogenicity objectives up to V02 (Day 31) will be conducted once data on all participants are available and an interim database lock has been conducted. The blind will be broken for the analysis and kept at the Sponsor level until the 6-month follow-up completion. No statistical adjustment is necessary because no hypotheses will be tested. A final analysis will be conducted once the 6-month safety data has been collected and the final database lock has occurred.

If the V01-V02 immunogenicity data release is planned at the time or after the 6-month safety data availability, only one database lock and one analysis including all data may be conducted.

5.7 Data Monitoring Committee (DMC)

The committee will assess the safety data in an unblinded manner. This includes the related AESIs and related SAEs review on ongoing basis, the safety analysis of data collected on at least 150 participants up to D31 (30 days after injection) as well as safety profile of each SP0202 formulation with all data up to D31.

5.8 Data Review for Statistical Purposes

No blind review of data will be performed.

